9.2 Safety

Routine safety and tolerability will be evaluated from the results of reported signs and symptoms, scheduled physical examinations, vital sign measurements, and clinical laboratory test results. More frequent safety evaluations may be performed if clinically indicated or at the discretion of the investigator.

Physical Examination

Complete and symptom-directed physical examinations will be performed by a licensed physician (or physician's assistant or nurse practitioner).

Vital Signs

Vital signs (blood pressure, respiratory rate, pulse rate and temperature) will be obtained per the study calendar.

Safety Laboratory Determinations

Laboratory evaluations will be performed as noted on the study calendar.

9.3 Stopping Rules/Interim Analysis

Safety was assessed after 1 cycle in the first 4 subjects to ensure that no more than one grade 3-5 drug reaction occurred and that no more than 4 of 6 subjects required a dose reduction for grade 2-4 drug reactions. At the initial dose of 150 mg daily, dose reductions to 150 mg every

other day for Grade 2 drug reactions were required. As such, the dosing schema was updated to the following:

The initial dose will be given at 150 mg po daily. If Grade 2 hematologic or non-hematologic toxicities attributable to the study drug are observed, three different, consecutive dose reduction levels may be utilized (below). All initial dose reductions will start at Level -1 and proceed to the next level if the toxicity in question persists. Dosing schedules will be dependent on what day of the week the patient starts the dose reduction level; for example, patients on Dose Level -1 with a Monday start would dose on Wednesday, Friday, Sunday, and so on.

- Level -1 (150 mg po every other day)
- Level -2 (150 mg po every three days)
- Level -3 (150 mg po twice a week)

Starting with patient 05, safety will be assessed to ensure that no more than 4 subjects (50% of the number of patients left to meet the enrollment target of 12) discontinue GDC-0449 after reducing to Level -3 due to adverse effects attributable to study drug. Safety will be reviewed monthly and at the time of each grade 3-5 reaction.

GDC-0449 will be discontinued under the following circumstance:

- If no more than 4 subjects (50% of the number of patients left to meet the enrollment target of 12) enrolled discontinue GDC-0449 after reducing to Level -3 due to adverse effects attributable to study drug.

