3.2 Number of Patients

Twelve patients will be enrolled in this study. Sample size: 12 patients. Accrual rate: 1-2 patients monthly.

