5.2.2 Preparation and Administration

Drug Administration: Patients should take GDC-0449 at approximately the same time according to their dose level, with or without food. If a patient misses a dose (e.g., due to emesis), he or she should be instructed not to take or make up that dose and to resume dosing with the next scheduled dose. Missed doses should not be made up.

Patient Care Implications: The terminal half-life of GDC-0449 is currently unknown, but is expected to be longer than 1 week, and may be as high as 2 to 3 weeks. If plasma levels of GDC-0449 need to be lowered emergently, animal studies suggest that oral administration of activated charcoal may lower drug plasma levels more quickly than dose cessation alone.

Drug Interactions: Avoid any concurrent drug metabolized by cytochrome P450 that has a narrow therapeutic index.

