6.1 Dose Modifications

In the case of any Grade 2 hematologic or non-hematologic toxicity attributable to the study drug, dose reductions can be performed to up to 3 different, consecutive levels as detailed below. All initial dose reductions will start at level -1, and proceed to the immediately lower level if the toxicity in question persists for at least 1 week. Dosing

schedules will be dependent on what day of the week the patient starts the dose reduction level; for example, patients on Dose Level -1 with a Monday start would dose on Wednesday, Friday, Sunday, and so on.

Dose reduction levels are:

- Level -1 (150 mg every other day)
 - Level -2 (150 mg every three days)
 - Level -3 (150 mg twice a week)
-
- GDC-0449 will be discontinued under the following circumstance:
 - Grade 3 or 4 non-hematologic or hematologic toxicity attributable to study treatment by Common Terminology Criteria for Adverse Events (CTCAE) version 4.

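### From patient 05 the only trial-level safety number in Section 9.3 is a cumulative cap of 4 counted stops that is not scaled to the number started, so 4 of 4 failures among patients 05-08 would not breach it

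*Combined protocol and SAP*

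**What the plan says.** Section 9.3 reports the limits used for the first 4 subjects in the past tense. From patient 05 onward the rule is that "safety will be assessed to ensure that no more than 4 subjects (50% of the number of patients left to meet the enrollment target", the target being 12. The event counted is to "discontinue GDC-0449 after reducing to Level -3 due to adverse effects attributable to study drug". On timing it adds: "Safety will be reviewed monthly and at the time of each grade 3-5 reaction". No number is attached to those reviews.

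The action bullet that follows has the direction reversed. The drug is to be discontinued "If no more than 4 subjects (50% of the number of patients left to meet the enrollment target of 12) enrolled discontinue GDC-0449", again counting stops that follow Level -3.

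Three other sections bear on how the cap works:

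- **Section 6.1** reduces the dose for attributable grade 2 toxicity. Patients "proceed to the immediately lower level if the toxicity in question persists for at least 1 week". The drug is stopped outright for "Grade 3 or 4 non-hematologic or hematologic toxicity attributable to study treatment".
- **Section 5.2.2** says the half-life "is expected to be longer than 1 week, and may be as high as 2 to 3 weeks".
- **Section 15.3** provides quarterly review by the full DSMC, and a halt if the DSMC or the principal investigator is concerned about unexpected safety issues.

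**The concern.** The cap expresses a 50% tolerance, but only against the final 8 patients. Early in the sequence a count of 4 can be a much higher proportion of those treated, and nothing says when an interim proportion is too high. Whether to keep enrolling after 3 of 3 or 4 of 4 failures is left to judgement.

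The existing reviews fit this event imperfectly. A counted stop usually follows persistent grade 2 effects, so the review tied to grade 3-5 reactions need not occur. The DSMC's stopping power is worded for unexpected issues, whereas muscle spasms, dysgeusia, fatigue and weight loss are listed in Section 14.3.1 as likely.

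The count is also narrow. A patient stopped under 6.1 for attributable grade 3-4 toxicity before reaching Level -3 does not enter it.

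What is at stake is protection of patients not yet enrolled. A late breach still takes treated patients off the drug.

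**Working it through.** **Reproducing the plan's figure.** The target is 12 (Section 3.2), 4 patients are already assessed (9.3), and 12 − 4 = 8. Half of 8 is 4, as stated. A breach of the monitoring sentence needs more than 4, that is, 5 counted stops. Five stops need five patients started from 05 onward, so patient 09 must have started (9 of 12 enrolled).

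**Inputs not in the plan (assumptions).** The true rate p of counted stops is taken as 20%, 40%, 50% or 70%. Time from start to counted stop is taken as 0.75 months, or uniform over 1-2, 1-4 or 2-6 months. The first value is a floor: three steps of at least 1 week, with 4 weeks to a month as in Section 8.4, give 3/4 = 0.75. The half-life points to slower stopping. Accrual is from Section 3.2: "Accrual rate: 1-2 patients monthly".

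**How often the gap would show.** The chance that patients 05-08 all fail is p⁴: 0.5⁴ = 0.0625 and 0.7⁴ = 0.240. The chance that the cap is ever breached, P(X ≥ 5 of 8), is 0.010, 0.174, 0.363 and 0.806 at p = 0.2, 0.4, 0.5 and 0.7.

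**A running version of the same tolerance.** Act when counted stops are at least 3 and exceed half of those started. The trigger is max(3, floor(n/2) + 1) = 3, 3, 3, 4, 4, 5 for n = 3 to 8 started. At n = 8 it equals the plan's own limit.

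**Exact check at the floor (1 per month, 0.75 months).** Each outcome is known before the next patient starts. With X_k the count among the first k, the running rule acts with probability

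P(X₄ ≥ 3) + P(X₄ = 2)·p + P(X₅ = 2)·p².

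- p = 0.7: 0.6517 + 0.2646 × 0.7 + 0.1323 × 0.49 = 0.902. The cap acts before patient 12 starts with probability P(X ≥ 5 of 7) = 0.647.
- p = 0.5: 0.3125 + 0.375 × 0.5 + 0.3125 × 0.25 = 0.578. The cap: 0.227.

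Mean number of patients not yet started when the rule acts, p = 0.7:

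- Running rule: first action at n = 3, 4, 5, 7 has probability 0.343, 0.3087, 0.1852, 0.0648, leaving 5, 4, 3, 1 patients. The sum is 3.57.
- Cap: fifth stop at n = 5, 6, 7 has probability 0.1681, 0.2521, 0.2269, leaving 3, 2, 1 patients. The sum is 1.24.
- Difference: about 2.3.

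**Simulation for slower stopping**, true 70%, rule checked at every counted stop:

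| Accrual | Months to stop | Acts before patient 12 starts: running / cap | Mean not yet started: running / cap |
|---|---|---|---|
| 1 per month | 0.75 | 90% / 65% | 3.6 / 1.2 |
| 1 per month | 1-2 | 78% / 42% | 2.4 / 0.6 |
| 1 per month | 1-4 | 57% / 19% | 1.4 / 0.2 |
| 1 per month | 2-6 | 16% / 2% | 0.2 / 0 |
| 2 per month | 0.75 | 78% / 42% | 2.4 / 0.6 |
| 2 per month | 1-2 | 42% / 8% | 0.8 / 0.1 |
| 2 per month | 1-4 | 5% / under 0.5% | 0.1 / 0 |
| 2 per month | 2-6 | 0% / 0% | 0 / 0 |

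If the running rule is checked only at monthly reviews, its 1-per-month figures fall to 78%, 56%, 28% and 2%. The check should therefore be made at each counted stop.

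**Where the running rule also fails.** If patients 05-08 all stop and no one else does, it fires in 100/100/100/42% of trials at 1 per month and 100/100/11/0% at 2 per month, in the order of times above. Newly started patients dilute the proportion.

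**The case against.** A reader might infer that the plan has no interim safety limit, or that four severe reactions in a row would pass unnoticed. The documents do not support either reading. The cap is cumulative, is looked at monthly and at each grade 3-5 reaction, and can act before enrolment ends. Attributable grade 3-4 toxicity stops the drug in that patient at once, and the DSMC meets quarterly. Four of four would be seen. What is missing is only an interim limit on the proportion.

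The case for leaving the rule alone is serious:

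- The counted event is mainly a tolerability failure with an approved drug, and a fixed cap is a defensible choice in a 12-patient pilot.
- The benefit depends on fast stopping. Scheduled visits are monthly for 3 months, then at months 4 and 6. If reductions followed those visits, a counted stop would fall at about months 4-6. Earlier contact is possible, since the calendar gives minimum visits, but the half-life also points to slow stopping.
- The proposed trigger ends in DSMC judgement too, and it leaves grade 3-4 stops before Level -3 uncounted.

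These points stand and lower the priority. They do not remove the gap: the reviews have no number for an interim proportion. A pause also differs from the present position, because enrolment waits for the judgement.

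**Conclusion.** The point holds in a limited form. The plan's 50% tolerance is written as a cumulative cap, so 4 of 4 failures among patients 05-08 would not breach it and the earliest breach is after patient 09 starts. This follows from the text of the monitoring sentence and needs no assumption beyond reading that sentence, rather than the reversed bullet, as the intended rule.

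The size of the gain rests wholly on assumed rates and times: 0 to about 2.3 patients not exposed. The upper end needs floor-time stopping, accrual of 1 per month and a true 70% rate together. With stopping at 2-6 months and a true 70%, it is about 0.2 patients at 1 per month and 0 at 2 per month. This is a low-priority improvement, below correcting the bullet.

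**What to change.** In this order:

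1. Correct the action bullet in Section 9.3 so that it acts when more than 4 subjects stop. As worded it would act at 0 to 4 and not at 5. Neither rule can operate until this is done.
2. Keep the cap of 4 and add: at each counted discontinuation, and at each monthly review, enrolment pauses for an ad hoc DSMC review, without waiting for the quarterly meeting, if counted stops among patients 05 onward are at least 3 and exceed 50% of those started. As a table: 3 stops with 3-5 started, 4 with 6-7, 5 with 8.

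The cost is one sentence or a three-row table, no extra visits, and possibly an unscheduled DSMC review. The downside is temporary pauses in 1-7% of trials at a true 20% (cap: 1%) and 17-37% at a true 40% (cap: 17%). The higher figures arise only when stopping is fast.

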Diagnosis and Main Eligibility Criteria	
Inclusion:
 
1. Patients with chronic GVHD diagnosed within 3 years after hematopoietic stem cell transplant (HSCT) for any disease, with any graft, and any conditioning regimen with at least one manifestation secondary to fibrosis, including: sclerodermatous skin changes, dry mouth, dry eye, esophageal strictures, or vaginal GVHD2. Failure to respond to corticosteroids, defined as:
• Progression of chronic GVHD despite optimal first line therapy (> 0.5 mg/kg/day of prednisone dose equivalent (PDE) for two weeks) or;• No improvement after 4-8 weeks of sustained therapy. Sustained therapy should include 2 weeks of > 0.5 mg/kg/day of PDE or;• Inability to taper steroid dosage to less than 0.5 mg/kg/day of PDE without worsening of chronic GVHD or;• Need for second or third line therapy beyond corticosteroids and calcineurin inhibitors or sirolimus, irrespective of other criteria listed under the current section 
Exclusion:
 
1. Patients who have had chemotherapy or radiotherapy within 4 weeks (6 weeks for nitrosoureas or mitomycin C) prior to entering the study or those who have not recovered from adverse events due to agents administered more than 4 weeks earlier.2. More than 2 lines of therapy beyond

	
corticosteroids with or without calcineurin inhibitors or sirolimus
 
3. Relapsed malignancy after transplantation

Study Product, Dose, Route, Regimen	
GDC-0449 will be given orally at 150 mg daily for a total of 6 months. Dosing will start at 150 mg daily. Dose reductions may be made in the case of intolerable toxicities that do not meet discontinuation criteria.
 
Dose Level -1: 150 mg every other day Dose Level -2: 150 mg every three days Dose Level -3: 150 mg twice a week
 
In patients who are responsive to therapy with acceptable toxicity, the treatment period will be extended to 12 months.

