15.3 Data and Safety Monitoring Plan

A Data and Safety Monitoring Committee (DSMC) is established at Huntsman Cancer Institute (HCI) and approved by the NCI to assure the well-being of patients enrolled on Investigator Initiated Trials that do not have an outside monitoring review. Roles and responsibilities of the DSMC are set forth in the NCI approved plan. The activities of this committee include a quarterly review of adverse events including SAEs, important medical events, significant revisions or amendments to the protocol, and approval of cohort/dose escalations. If the DSMC and/or the PI have concerns about unexpected safety issues, the study will be stopped and will not be resumed until the issues are resolved. The DSMC also reviews and approves audit reports generated by the Research Compliance Office.

This study will be reviewed by the full committee at each quarterly DSMC meeting. This includes a review of all serious adverse events (SAEs) occurring in patients treated at HCI or its affiliates as well as all grade 3 or greater toxicities for patients on treatment and within 30 days follow-up window (only if possibly, probably or definitely related).

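### From patient 05 the only numerical stopping limit in 9.3 counts drug-related stops after Level -3 alone, so the Grade 3-4 stops that 6.1 requires at higher doses, and drug-related deaths there, never count

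*Combined protocol and SAP*

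**What the plan says.** Section 9.3 describes two stages. The first, in the past tense, was a check after one cycle in the first 4 subjects, partly "to ensure that no more than one grade 3-5 drug reaction occurred". The second starts with patient 05. It allows no more than 4 subjects, stated as half of those still to be enrolled, to "discontinue GDC-0449 after reducing to Level -3 due to adverse effects attributable to study drug". The same qualifier appears in the bullet that gives the consequence. Section 9.3 adds: "Safety will be reviewed monthly and at the time of each grade 3-5 reaction".

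Section 6.1 gives two routes. For lower-grade toxicity: "In the case of any Grade 2 hematologic or non-hematologic toxicity attributable to the study drug, dose reductions can be performed", starting at Level -1 and moving down one level at a time. For severe toxicity the drug is discontinued, the trigger being "Grade 3 or 4 non-hematologic or hematologic toxicity attributable to study treatment by Common Terminology Criteria for Adverse Events (CTCAE) version 4". No dose level is named and no prior reduction is required. The Study Summary draws the same line: "Dose reductions may be made in the case of intolerable toxicities that do not meet discontinuation criteria".

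Section 15.3 provides quarterly DSMC review, including "all grade 3 or greater toxicities for patients on treatment and within 30 days follow-up window (only if possibly, probably or definitely related"), and a halt based on judgement: "If the DSMC and/or the PI have concerns about unexpected safety issues, the study will be stopped and will not be resumed" until they are resolved.

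**The concern.** A numerical stopping limit should become easier to cross as the drug proves more toxic. Here the counted event lies at the end of a ladder that only Grade 2 toxicity leads down. A patient with attributable Grade 3 or 4 toxicity before Level -3 leaves treatment as 6.1 directs, is not counted, and can no longer become a counted case. Severe early toxicity therefore shrinks the pool from which the count is drawn.

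The practical stake is the decision to pause. With several of the last 8 patients off drug for severe attributable toxicity, the study could correctly record that its stopping limit had not been crossed. The decision would then rest on judgement, with no pre-set number to prompt it.

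**Working it through.** **Inputs from the documents.** Enrollment target 12 (3.2). The current rule starts with patient 05, so 12 − 4 = 8 patients remain (9.3). No replacement of patients is described.

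**The plan's own figure.** 0.50 × 8 = 4, which reproduces the stated limit. Read as a ceiling of 4, it is crossed at the fifth counted patient.

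**Which events count.**

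| Event in patients 05-12 | Drug stopped under 6.1? | Counted in 9.3? |
|---|---|---|
| Attributable Grade 3-4 at 150 mg daily, Level -1 or Level -2 | Yes | No |
| Drug-related death at those levels | Not listed (6.1 names Grades 3 and 4) | No |
| Attributable Grade 3-4 at Level -3 | Yes | Yes |
| Stop for attributable Grade 2 toxicity after reaching Level -3 | Not mandated | Yes |

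**Logical limits, with no assumed rates.** If k of the 8 have an uncounted event, at most 8 − k can still be counted. Crossing needs 5, so k = 4 leaves at most 4 and crossing is impossible. With k = 8 the count is 0 of 8.

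**Illustration.** The documents give no toxicity rates for this population, so two are assumed:
- p = probability of an attributable Grade 3-5 reaction before Level -3;
- r = probability that a patient without such a reaction stops for drug toxicity after reaching Level -3.

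Patients are taken as independent. As written, a patient is counted with probability (1 − p)r. With both kinds of event pooled, it is p + (1 − p)r. The chance of crossing is P(X ≥ 5) for X binomial with n = 8. For example, p = 0.20 and r = 0.20 give 0.80 × 0.20 = 0.16 as written, so P = 0.0038, and 0.20 + 0.16 = 0.36 pooled, so P = 0.118.

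The highest value, p = 0.43, is an upper illustration. Section 2.5 reports that in the phase 2 basal-cell carcinoma trial all patients had an adverse event and 57% had only Grade 1 or 2, so 100 − 57 = 43% had something worse. That figure is any-cause and from a different population.

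With r = 0.20:

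| p | Counted, as written | P(cross), as written | Counted, pooled | P(cross), pooled |
|---|---|---|---|---|
| 0.10 | 0.180 | 0.65% | 0.280 | 4.4% |
| 0.20 | 0.160 | 0.38% | 0.360 | 12% |
| 0.30 | 0.140 | 0.21% | 0.440 | 24% |
| 0.43 | 0.114 | 0.08% | 0.544 | 46% |

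As p rises, the chance of crossing falls under the current wording and rises under the pooled count. For p from 0.10 to 0.30 and r from 0.10 to 0.30, the ranges are 0.008% to 3.8% as written and 0.8% to 39% pooled.

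**The case against.** The strongest defense is that 9.3 divides the work on purpose. Grade 2 reactions in the first subjects led to the reduction ladder, and the limit asks whether that ladder fails. Severe reactions are handled individually by mandatory discontinuation and collectively by a review that the first Grade 3-5 reaction already triggers. For a 12-patient, single-center pilot of a drug approved in another indication, that is a defensible structure.

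Oversight also extends beyond 9.3 and 15.3. Section 14.2 sends serious adverse events to the DSMC, FDA, IRB and NCI. Section 14.4 requires 24-hour notification to NCI of serious Grade 3-5 events, with a full report within 5 days, subject to the listed protocol exceptions. It requires expedited reporting of on-study deaths regardless of cause, with limited exceptions. Section 10.2 commits to summarizing adverse and serious adverse events, so a report that follows the plan would show severe toxicity alongside any statement about the limit.

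Most of this stands. A reader might infer that severe toxicity goes unmonitored after patient 04; the documents do not support that, because review is mandatory and prompt. A reader might also infer that no Grade 3-4 stop can count; one at Level -3 does. And a reader might infer that the earlier allowance of one Grade 3-5 reaction should still apply. It was a one-cycle check in 4 subjects, and nothing extends it to 8 patients treated for 6 to 12 months.

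What the defense does not supply is a number. Each of these provisions ends in judgement, and the 15.3 halt is framed around unexpected issues, although fatigue, weight loss and muscle spasms are listed as likely in 14.3.1. Even as a test of the ladder, the limit becomes harder to reach as early severe toxicity removes patients from it.

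**Conclusion.** The point holds for the numerical limit and goes no further. From patient 05, mandated Grade 3-4 stops before Level -3 and drug-related deaths before Level -3 are outside the only stated count. Zero of 8 is possible with every patient stopped for severe toxicity, and four such events make the limit unreachable. These two results need no assumed rates. They rest on reading the limit as more than 4 and on 8 patients with no replacement. The bullet in 9.3 attaches its consequence to no more than 4 subjects discontinuing, which reverses the sense of the preceding paragraph. That is a separate wording fault, and the excluded events are the same either way.

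The crossing probabilities are illustrative and depend on the assumed p and r. It is worth correcting in the next amendment because the rule responds in the wrong direction to severe toxicity and the correction is small.

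**What to change.** In 9.3, replace "discontinue GDC-0449 after reducing to Level -3 due to adverse effects attributable to study drug" in both places with wording that counts any subject who stops GDC-0449 at any dose level because of a drug-attributable adverse effect, expressly including stops required by 6.1, or who dies of a drug-attributable event. Keep the limit at no more than 4 of the 8. Report discontinuations by grade and by dose level at stopping.

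This is one sentence of rule text and can go in with the correction of the bullet. Grade, attribution and permanent discontinuation for an adverse event are already recorded under 14.1.1, so no new data are needed.

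The downside is a possible earlier pause, with the pooled probabilities shown above (about 4% to 46% at r = 0.20). The new count would also include drug-attributable Grade 2 stops before Level -3, which those figures do not model. The number 4 was set for ladder failure, so the sponsor should confirm that it is acceptable for the wider set of events. The pooled limit would still tolerate four severe reactions or deaths. Whether to add a separate, lower Grade 3-5 limit is a trade-off for the sponsor and is not part of this fix.

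### The last bullet of Section 9.3 reverses the study-level stopping rule: the tolerable count is written as the trigger for discontinuing GDC-0449

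*Combined protocol and SAP*

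**What the plan says.** Section 9.3 first reports, in the past tense, how the first 4 subjects were assessed, including a check "to ensure that no more than one grade 3-5 drug reaction occurred". It then introduces three reduced dose levels and a new rule from patient 05 on.

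The new rule appears twice. As a monitoring aim, "safety will be assessed to ensure that no more than 4 subjects" discontinue after reduction to Level -3 for drug-attributable adverse effects; the number is explained as 50% of the patients still needed to reach 12. Then, under the lead-in "GDC-0449 will be discontinued under the following circumstance", the single bullet reads "If no more than 4 subjects (50% of the number of patients left to meet the enrollment target of 12) enrolled discontinue GDC-0449", followed by the same Level -3 and attribution condition.

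On timing, the section adds: "Safety will be reviewed monthly and at the time of each grade 3-5 reaction". Section 5.7 (Criteria for Removal from Study) sends the reader to Section 9 for the early stopping criteria.

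**The concern.** The same condition serves as the aim and as the trigger. A count of 4 or fewer cannot be both what monitoring is meant to secure and the circumstance in which the drug is stopped. The parenthesis and the event definition match in both places, so the aim seems to have been carried into the bullet without being negated.

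The bullet cannot be read as a rule for individual patients, because it counts subjects. The individual rule is in Section 6.1, which discontinues the drug for "Grade 3 or 4 non-hematologic or hematologic toxicity attributable to study treatment". Nothing elsewhere restates or corrects the count.

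The monitoring sentence does not say what happens if the limit is passed; only the bullet does. Anyone applying the operative text, such as the DSMC or the IRB, has to set its wording aside to reach the intended decision.

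**Working it through.** **Inputs**
- Enrollment target 12 (Section 3.2: "Twelve patients will be enrolled in this study").
- New rule starts with patient 05, so 4 patients precede it (Section 9.3).
- Limit 4, described as 50% of the patients left to enroll (Section 9.3).
- Per-patient probability p of discontinuing after Level -3 for attributable adverse effects: not given in the documents. It is an assumption, shown over a range.

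**1. Reproduce the limit.** Patients left: 12 - 4 = 8. Half of them: 0.5 × 8 = 4. This matches the plan. Counted over all 12 patients, 4 would be 4/12 = 33%, which does not match the stated 50%. The count therefore belongs to patients 05 to 12.

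**2. Set the two statements side by side.**

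| Discontinuations among the 8 | Monitoring sentence | Bullet as written |
|---|---|---|
| 0 to 4 | acceptable | trigger met: discontinue GDC-0449 |
| 5 to 8 | limit exceeded | trigger not met |

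The two disagree at every possible count.

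**3. Apply the written bullet on the protocol's own schedule.** Reviews are monthly. At the start of the rule the count is 0, and 0 ≤ 4, so the trigger is met at the first review. This holds for any p and needs no probability calculation.

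**4. Apply the reworded bullet (more than 4).** With X binomial on n = 8, the limit is exceeded when X ≥ 5:

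P(X ≥ 5) = Σ (k = 5 to 8) C(8,k) p^k (1-p)^(8-k)

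For example, at p = 0.50: (56 + 28 + 8 + 1)/256 = 93/256 = 0.3633.

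| Assumed p | P(X ≥ 5 of 8) |
|---|---|
| 0.10 | 0.0004 |
| 0.30 | 0.0580 |
| 0.50 | 0.3633 |
| 0.80 | 0.9437 |

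A cumulative count cannot fall, so the chance of exceeding the limit at some review equals the chance of exceeding it by the final count. The probability rises with p, as a tolerability limit should.

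**5. Check the neighboring wordings.**
- *4 or more* would stop at a count that the monitoring sentence allows. It gives 0.194 instead of 0.058 at p = 0.30, and 0.637 instead of 0.363 at p = 0.50.
- *More than 4* counted over all 12 patients gives 0.0043, 0.276 and 0.806 at p = 0.10, 0.30 and 0.50, against 0.0004, 0.058 and 0.363 over 8. The denominator is worth stating.

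**The case against.** The strongest reply is that this is a dropped negation that nobody would follow. The sentence just above gives the limit and its direction, and a trigger already met at zero events cannot be operated as written. Other safeguards do not depend on the bullet: individual discontinuation under Section 6.1, review monthly and at each grade 3-5 reaction, and, under Section 15.3, quarterly full-committee review of serious adverse events "as well as all grade 3 or greater toxicities for patients on treatment" when at least possibly related. Section 15.3 also stops the study if the DSMC or the investigator has concerns about unexpected safety issues.

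This stands as a limit on the likely harm. It does not rescue the bullet, because none of these safeguards attaches a consequence to a number.

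It can also be said that the bullet refers to subjects enrolled and does not expressly leave out patients 01 to 04. That is a fair observation on the wording. The start at patient 05 and the 50% arithmetic favor counting patients 05 to 12, but the text should say so.

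A reader might infer that the written rule is most likely to stop the drug when it is best tolerated, because P(X ≤ 4 of 8) is 0.9996 at p = 0.10 and only 0.06 at p = 0.80. The documents do not support that. Those figures describe one look at the final count, whereas review is monthly and the literal trigger is met at the first review at every rate.

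A reader might also infer that the lack of a numeric grade 3-5 limit from patient 05 on is an error. It is not: such events are handled by individual discontinuation and by review, and adding a number would be a design preference.

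**Conclusion.** The bullet is wrong as written and must be corrected. It inverts the only study-level rule that ties a consequence to a numeric limit from patient 05 on. Read literally, it calls for discontinuation with no events and does not call for it at 5 to 8 of 8.

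The inversion is a matter of logic and rests on no assumed rate. The probabilities for the reworded bullet do rest on assumptions: the rates shown, independence between patients, and all eight remaining patients being enrolled and followed. They illustrate how the intended rule behaves.

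The finding does not extend to a claim that patients are left unprotected. The intent is recoverable and the other safeguards remain.

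**What to change.** In the last bullet of Section 9.3, replace *no more than 4 subjects* with *more than 4 subjects*, and state that the count covers patients 05 to 12. Keep the Level -3 and attribution conditions as they are. The monitoring sentence needs no change.

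The cost is a short wording change in a protocol amendment, with no added patients, visits or data.

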5.7 Criteria for Removal from Study

Patients will be removed from study when any of the criteria listed in [Section 5.5](#) applies. The reason for study removal and the date the patient was removed must be documented in the Case Report Form. In addition, early stopping criteria are defined in Section 9.

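### The trial-level stopping bullet in Section 9.3 is inverted: as written it triggers at 0 to 4 Level -3 discontinuations and not at 5 or more

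*Combined protocol and SAP*

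**What the plan says.** Section 9.3 first reports, in the past tense, a safety check on the first 4 subjects, after which the dosing schema was updated to three reduction levels. It then sets the limit for the rest of the trial: "Starting with patient 05, safety will be assessed to ensure that no more than 4 subjects (50% of the number of patients left" to reach the target of 12) come off the drug "after reducing to Level -3 due to adverse effects attributable to study drug". Safety is to be reviewed monthly and at each grade 3-5 reaction.

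The stopping rule follows. Under the lead-in "GDC-0449 will be discontinued under the following circumstance" there is a single bullet, which begins "If no more than 4 subjects (50% of the number of patients left to meet the enrollment target of 12) enrolled discontinue GDC-0449" and ends with the same Level -3 wording.

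Section 5.7 sends the reader to this part of the protocol: "In addition, early stopping criteria are defined in Section 9". Section 6.1 holds a separate rule for the individual patient, who stops for "Grade 3 or 4 non-hematologic or hematologic toxicity attributable to study treatment". Section 15.3 adds a general power: "If the DSMC and/or the PI have concerns about unexpected safety issues, the study will be stopped", and not resumed until the issues are resolved.

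**The concern.** The same phrase, no more than 4, serves as the acceptable state in one sentence and as the stopping condition in the next. Both cannot be meant. Applied as written, the bullet calls for stopping while nobody has discontinued, and it has no trigger when a fifth patient does.

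The wording is operative. The check on the first 4 subjects is reported as done, so this bullet is the only count-based, trial-level trigger still in force in the section to which 5.7 refers. Tolerability is also a live question, since 9.3 reports that dose reductions for grade 2 reactions were needed at the starting dose of 150 mg daily. A stopping rule should be executable as it stands, without the reader having to reverse it.

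**Working it through.** **Inputs**

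- Enrollment target: 12 (Section 3.2).
- Subjects already assessed when the current rule begins: 4 (Section 9.3).
- Stated limit: 4, described as 50% of the patients left (Section 9.3).
- Discontinuation rate, error rate or power for the rule: none given. Section 10.2 says adverse events are summarized descriptively only. Any rate used below is therefore an assumption.

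**Step 1: reproduce the stated limit.** Patients left = 12 - 4 = 8, and 0.5 x 8 = 4. The plan's figure reproduces exactly. A base of all 12 does not give it: 0.5 x 12 = 6, and 4/12 = 33%. The arithmetic fits patients 05-12.

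**Step 2: set the two statements side by side.** Let X be the number of patients 05-12 who discontinue after reaching Level -3 because of attributable adverse effects.

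| X | Sentence setting the limit | Bullet as written |
|---|---|---|
| 0 to 4 | acceptable, continue | stop |
| 5 to 8 | limit exceeded | no stop |

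The conditions X <= 4 and X >= 5 are complements, so the two statements disagree at all 9 possible values of X. No other section states the rule the right way round.

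**Step 3: illustrate the direction of the error.** Assume X follows a binomial distribution with n = 8 and a common probability p. Then

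P(X <= 4) = sum over k = 0 to 4 of C(8,k) p^k (1 - p)^(8 - k), and P(X >= 5) = 1 - P(X <= 4).

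For example, at p = 0.5: (1 + 8 + 28 + 56 + 70)/256 = 163/256 = 0.637.

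| Assumed p | Literal condition met, P(X <= 4) | Intended condition met, P(X >= 5) |
|---|---|---|
| 0.10 | 0.9996 | 0.0004 |
| 0.20 | 0.990 | 0.010 |
| 0.30 | 0.942 | 0.058 |
| 0.50 | 0.637 | 0.363 |
| 0.60 | 0.406 | 0.594 |
| 0.70 | 0.194 | 0.806 |

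These refer to the final count in all 8 patients. The literal condition is met less often as tolerability worsens, which is the wrong direction for a safety rule. Because X starts at 0, the literal condition already holds at the first monthly review, whatever p is.

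**The case against.** The strongest reply is that nobody would apply the bullet literally. Stopping a drug because no one has discontinued is absurd, and the correct limit stands directly above it. That is fair, and it is why the practical harm is small. It does not make the bullet right, and 5.7 directs readers to Section 9 for the criteria.

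Other protections also stand. A patient with attributable grade 3 or 4 toxicity stops under 6.1, safety is reviewed monthly and at each grade 3-5 reaction under 9.3, and the DSMC or the PI can halt the study under 15.3. A reader might infer that the trial has no working safety stop, but these provisions show otherwise. What they do not supply is a count threshold.

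The counted event is also narrow. Toxicity must carry a patient down three consecutive levels, with at least 1 week of persistence before each further step (6.1), and then lead to discontinuation. The higher values of p in the table are therefore illustrative only.

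A reader might further infer that the set of patients counted is unresolved, because the bullet says only that the subjects are enrolled and so might cover all 12. The documents do not support that reading. The bullet and the sentence above it both tie the limit to half of the patients left, which gives 4 from 8, and the sentence begins with patient 05. A slight ambiguity remains: that opening could describe when monitoring begins, and patients 01-04 are not expressly excluded. Putting a probability on the two bases leading to different decisions would need a Level -3 discontinuation rate for patients 01-04. The documents give none, and do not show whether any of them reached that level, so no such figure is offered.

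**Conclusion.** The bullet is wrong as written. Its condition is the exact reverse of the limit in the preceding sentence, and the intended trigger is 5 or more of the 8 patients 05-12. This conclusion rests on the text alone and is firm. The probabilities in the table rest on an assumed common rate and independence between patients, and show only the direction and scale of the error.

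The severity is low: a drafting contradiction in a safety rule, whose intended direction is evident and which other safeguards back up. It is worth correcting because the text is operative and the correction is small. The choice of 4 of 8 as a limit is not in question here.

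**What to change.** Reword the bullet so that GDC-0449 is discontinued if more than 4 (that is, 5 or more) of patients 05-12 stop the drug "after reducing to Level -3 due to adverse effects attributable to study drug". In the preceding sentence, replace the reference to subjects with patients 05-12 as well, so that the limit and the trigger name the same group. This also removes the slight ambiguity left by the word enrolled.

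The cost is a wording amendment to two sentences in 9.3, with IRB review and approval under 15.4. It needs no new data, visits or patients, and the intended limit of 4 of 8 does not change.
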